Our laboratory has pioneered the use of moderate intensity RMT regimens to provide respiratory muscle resistance training and address progressive neuromuscular weakness (Jones et al, 2011, 2014, 2016). Counteracting respiratory muscle weakness with moderate intensity exercise offers a biologically plausible mechanism to target progressive inspiratory and expiratory muscle weakness in ALS. This research will be the first study of a comprehensive RMT program targeting both inspiratory muscle weakness with IMT and expiratory muscle weakness with EMT in individuals with ALS. We will also utilize a well-defined, moderate intensity RMT regimen and pioneer the use of patient-reported RPE to monitor and regulate intensity. We will use telehealth visits to collect measures of respiratory muscle strength (maximum inspiratory pressure [MIP], maximum expiratory pressure [MEP]) in order to 1) reduce the number of on-site visits required by participants and 2) improve our ability to collect repeated measures of our primary outcomes. We will continue to use the novel modifications, methods, and technologies we have developed to allow progressive, individualized, and calibrated RMT to be delivered across the range of human performance. These include our calibration methodology to ensure accurate, precise RMT pressure-threshold resistance (Jones et al., 2014, 2016) and the Inspiratory Adapter 150 (US Patent Pending) to allow use of expiratory-type devices for IMT (EMST 150; Aspire LLC) and expand the range of resistance.

The results of this study will be used to refine our RMT in ALS treatment regimen, select appropriate outcome measures, and develop the statistical analysis plan for use in a future NIH grant application to further study RMT in ALS in a larger group of subjects.

4. Design & Procedures:

Participants will be recruited from the Duke ALS Clinic or referred through CT.gov or outside hospitals. Twelve adults will participate in a single- subject A₁-B-A₂ study involving 4 visits to Duke over 24 weeks (see **Figure 1**). The 6 week delayed start period represented by A₁ will establish baseline status prior to initiation of RMT and A₂ will determine detraining effects over 6 weeks of RMT withdrawal. Participants will complete four 3-week cycles of progressive RMT during the B phase. We will measure

Moderate intensity respiratory muscle training (RMT) in ALS

NCT04224961

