MIP and MEP weekly. To reduce participant burden and enhance our ability to obtain repeated measures, we will have the ability to obtain measurements of MIP and MEP during web-based telehealth visits.

Participants will complete a full assessment during the first study visit (M1), which may be performed in person or remotely via a web-based session, and receive training/instruction for obtaining MIP and MEP measurements at home with a portable, battery-powered digital pressure gauge manometer (MicroRPM Pressure Meter; Micro Direct). Prior to the pretest visit, participants who opt for remote visits will be mailed instructions for the home-based RMT regimen and the devices as well as a written treatment log. The pretest visit (M7) will include a full assessment after which RMT will commence. During the B phase, participants will complete 12-weeks of moderate intensity RMT, divided into four 3-week cycles, and participate in weekly web-based RMT therapy visits (M8-M18). Posttest assessment (M19) will occur immediately following completion of the 12-week RMT regimen. We will measure MIP and MEP during RMT withdrawal via web-based telehealth visits (M20-24). Following the fourth and final full assessment visit (M25), participants will return all equipment and will be offered the opportunity to initiate a clinical RMT regimen and receive follow-up care by Speech Pathology during future ALS Clinic visits.

Week	A1 (6 weeks)						B (12 weeks)												A2 (6 weeks)							
	0	1	2	3	4	5	6	7	8	9	10	11	12	13	14	15	16	17	18	19	20	21	22	23	24	
Measurement	M 1*	M 2 ^T	M 3 ^T	M 4 ^T	M 5 ^T	M 6 ^T	M 7*	M 8 ^T	M 9 ^T	M 10 ^T	M 11 ^T	M 12 ^T	M 13 ^T	M 14 ^T	M 15 ^T	M 16 ^T	M 17 ^T	M 18 ^T	M 19*	M 20 ^T	M 21 ^T	M 22 ^T	M 23 ^T	M 24 ^T	M 25*	
MIP	X	X	X	X	X	X	X	X	X	X	X	X	X	X	X	X	X	X	X	X	X	X	X	X	X	
MEP	X	X	X	X	X	X	X	X	X	X	X	X	X	X	X	X	X	X	X	X	X	X	X	X	X	
SNIP	X						X													X						X
PCF	X						X													X						X
ALSFRS	X						X													X						X
EAT-10	X						X													X						X
SF36	X						X													X						X
WHOQOL-BREF	X						X													X						X
CES-R	X						X													X						X
RMT							X	X	X	X	X	X	X	X	X	X	X	X	X	X	X	X	X	X	X	
	PRE						POS																			
	RMT Cycle 1						RMT Cycle 2						RMT Cycle 3						RMT Cycle 4							

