Participants will be asked to keep a paper log documenting the number of repetitions they complete each day as well as RPE and any pain they experience associated with home RMT.

See **Figure 4** and **Figure 5** for a detailed treatment decision tree and sequential list of treatment activities for each study visit.

10. Risk/Benefit Assessment:

Research participation is expected to be safe and well-tolerated based on our prior research using moderate intensity RMT in late-onset Pompe disease (Jones et al, 2011, 2014, 2016) and the relevant research in the ALS literature (Cheah et al., 2009; Pinto et al., 2012; Plowman et al., 2016). Multiple elements of our study design have been included to ensure rigorous safety monitoring and minimize risk including:

- Individualized, stepwise pressure-threshold resistance based on each subject's respiratory muscle strength and RPE;
- Weekly contact with the RMT clinician during the 12-week training period to foster adherence and assess for any negative side effects;
- A predetermined algorithm for modulating RMT intensity to ensure participant safety;
- Use of an experienced RMT clinician to conduct the RMT program with training and oversight by the PI;
- Calibration of RMT devices to ensure precise and accurate pressure-threshold resistance.

11. Costs to the Subject:

There are no costs to subjects to participate in this study.

12. Data Analysis & Statistical Considerations:

Descriptive statistics will be provided for all outcomes. Primary outcome measures of MIP and MEP will be analyzed using visual analysis of raw data in graphical format using the method described by Land and Gast (2014). Magnitude of change for our primary outcome measures will be determined using

Moderate intensity respiratory muscle training (RMT) in ALS

NCT04224961

Cohen's measure of effect size (d) as defined by the first equation for single-subject d provided by Busk and Serlin (1992). Simply stated, d is obtained by subtracting the mean of the first assessment from the mean of the second assessment, divided by the standard deviation of the first assessment. Effect size calculations will be determined to compare results from baseline (M0-M5) to withdrawal (M19-M24) and pretest (M7) to posttest (M18). We will use conservative interpretation guidelines for effect size calculations in which $d < 0.6$ is negligible, $d \geq 0.6$ modest, $d \geq 1.0$ large, and $d \geq 2.0$ very large.

13. Data & Safety Monitoring:

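### No rule assigns the boundary readings M7 and M19 to a phase, and Figure 1's header and Section 12's windows place them against their training exposure

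*Combined protocol and SAP*

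**What the plan says.** Section 4 defines the phases by training status. For the first, "The 6 week delayed start period represented by A₁ will establish baseline status prior to initiation of RMT"; for the last, "A₂ will determine detraining effects over 6 weeks of RMT withdrawal". Between them, "During the B phase, participants will complete 12-weeks of moderate intensity RMT, divided into four 3-week cycles".

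The two visits at the phase changes are described by timing only:

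- M7 (week 6): "The pretest visit (M7) will include a full assessment after which RMT will commence". Section 9 agrees that training begins once the M7 assessments are done.
- M19 (week 18): "Posttest assessment (M19) will occur immediately following completion of the 12-week RMT regimen".

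Section 4 names M8-M18 as the weekly therapy visits and M20-M24 as the telehealth readings during withdrawal, with M25 as the final full assessment. M7 and M19 are in neither list.

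In Figure 1, the header starts A1 at week 0, B at week 6 and A2 at week 18. M7 therefore falls under B and M19 under A2.

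Section 12 states that "Primary outcome measures of MIP and MEP will be analyzed using visual analysis of raw data in graphical format". It adds effect sizes comparing baseline (M0-M5) with withdrawal (M19-M24), and pretest (M7) with posttest (M18). It gives no rule for allocating readings to phases.

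**The concern.** Comparing a person's own readings between phases is this design's evidence for a training effect and for detraining. Any comparison of level, overlap or neighbouring points needs every reading to have a phase.

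M7 reflects no training and M19 reflects the whole regimen. If M7 is read as a training point and M19 as a withdrawal point, a real gain looks smaller and later, and withdrawal appears to start from the trained peak. If nothing is fixed in advance, the allocation can be settled after the graphs have been seen. The results are also meant to inform the analysis plan of a larger study.

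**Working it through.** **1. The plan's own durations.** M7 is at week 6, M19 at week 18 and M25 at week 24. The phases last 6-0 = 6, 18-6 = 12 and 24-18 = 6 weeks, as stated. The repetitions agree: 4 × (125+250+375) = 3000 for each muscle group.

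**2. Where the ambiguity arises.** Weekly readings at weeks 0 to 24 number 25, while 6+12+6 = 24. Figure 1's blocks hold 6 (M1-M6), 12 (M7-M18) and 7 (M19-M25) readings. Grouping by exposure gives 7 (M1-M7), 12 (M8-M19) and 6 (M20-M25).

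**3. Section 12's windows.**
- Labels as in Figure 1: M0 does not exist, so baseline is M1-M5 and omits M6 and M7. Withdrawal includes M19 and omits M25.
- Labels counted from 0: baseline is weeks 0-5 (Figure 1's M1-M6) and withdrawal is weeks 19-24 (Figure 1's M20-M25). Withdrawal is then correct, but the untrained week-6 reading is still left out of the baseline mean and SD.

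**4. Effect of the grouping.** The documents give no trajectory. I assume no noise, a flat A1, a linear gain G over weeks 6-18 and a linear loss L over weeks 18-24.

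| Quantity | Figure 1 blocks | By exposure |
|---|---|---|
| Mean of B minus A1 | (0+1+…+11)/(12×12) G = 0.458G | (1+2+…+12)/(12×12) G = 0.542G |
| Mean of A2 | G - (0+…+6)/(7×6) L = G-0.500L | G - (1+…+6)/(6×6) L = G-0.583L |
| First step into A2 | M18 to M19: +G/12 | M19 to M20: -L/6 |
| First-to-last fall within A2 | L | 5L/6 |

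B minus A1 is lower by G/12, which is 0.083/0.542 = 15% in relative terms. The withdrawal window M19-M24, with labels as in Figure 1, has mean G - (0+…+5)/(6×6) L = G-0.417L, against G-0.583L for M20-M25.

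**5. Does A2 minus B change sign?** Figure 1 blocks give 0.542G-0.500L. Exposure gives 0.458G-0.583L, which is negative only if L > 0.458/0.583 = 0.79G.
- L = G: +0.042G against -0.125G (sign changes).
- L = 0.5G: +0.292G against +0.167G (no change).
- Gain complete by week 12, L = 0.5G: B means are 8.5/12 = 0.708G and 9.5/12 = 0.792G, A2 means are 0.750G and 0.708G, so the difference is +0.042G against -0.083G (sign changes).

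**6. No training effect.** With a steady decline of 0.02 units per week, B minus A1 is -0.02 × (11.5-2.5) = -0.18 with Figure 1 blocks and -0.02 × (12.5-3.0) = -0.19 by exposure.

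**7. Value of M7 in the baseline.** With independent normal readings, no true change, n baseline and 6 withdrawal readings, P(d ≥ 1.0) is the upper tail of t with n-1 degrees of freedom at 1/√(1/n+1/6). For n = 6 this is 7.2%; for n = 7 it is 6.1%.

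**The case against.** A reader might infer that Figure 1 contradicts the text on when training starts and ends, that the visual analysis must therefore understate the gain, and that detraining is hidden. The documents do not support this.

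- **No contradiction in time.** Figure 1 is a study overview. As calendar spans, its blocks match the text: B runs from week 6 to week 18 and A2 from week 18 to week 24. M7 is also the first training session, once its assessments are done, and the figure key has separate labels for the pretest and posttest visits.
- **No stated link to the analysis.** Section 12 never says that readings are grouped by that header, and specifies no phase-B mean or B-minus-A1 contrast. A raw weekly graph still shows M7 and M19 in order.
- **Detraining is not hidden in the trend.** With M19 in A2, the within-phase fall is the full L; without it, 5L/6.
- **The direction is not general.** With no effect and steady decline, Figure 1's blocks are slightly favourable (-0.18 against -0.19).
- **The table is imperfect evidence.** In the text copy, the third and fourth SNIP marks fall one column to the right of M19 and M25, and RMT marks run to week 24. The header's 6 and 12 columns do equal the stated durations.
- **M7 has its own role as pretest anchor,** and adding it to the baseline gains little (7.2% to 6.1%).

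All of this stands, and it limits the point to a conditional one. It does not supply the missing rule. Nor does it repair Section 12's windows, which omit M7 under either way of counting and, with labels as in Figure 1, mix a fully trained reading into withdrawal. M7 can anchor the pretest comparison and still count as an untrained reading.

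**Conclusion.** The point holds in a limited form. M7 is untrained, M19 is fully trained, and nothing assigns either to a phase. The only per-visit phase layout, and Section 12's withdrawal window with labels as in Figure 1, put M19 on the withdrawal side; that layout puts M7 on the training side, and Section 12 leaves it out of the baseline mean and SD.

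The bias is conditional on grouping the readings this way and on training raising strength. Under the assumed linear path, B minus A1 is understated by about 15%, the first step into A2 shows a rise of G/12 where exposure gives a fall of L/6, and the withdrawal mean as written is too high by L/6 (0.583L-0.417L). A change of sign in A2 minus B needs near-complete loss (about 79% or more of a linear gain) or an early plateau. The trend within A2 is not masked. The problem is modest for a 12-person pilot with no hypothesis test, but worth correcting because the correction is nearly free.

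**What to change.** State in Section 12 that phases follow training exposure: A1 = M1-M7, B = M8-M19, A2 = M20-M25. Use these sets for the MIP and MEP graphs and for the baseline and withdrawal means and SD, with visit labels that match Figure 1. In Figure 1, place the phase-change lines after M7 and after M19.

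The cost is a few lines of wording and two moved lines. No visit, measurement or part of the training schedule changes. There are two small downsides. M7 and M19 may be on-site readings within mostly telehealth phases, so mark them on the graphs. The fall within A2 is then counted from M20, so M19 should stay visible just before the line.

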agrees, consent will be obtained. Consent will take place via phone script with eConsent, which is available via REDCap. This functionality provides the ability to consent remote participants or participants in clinic via tablets or touchscreen device. Participants will have the capability to sign electronically with a stylus, mouse, or finger. Once the consent form is submitted, participants will receive an email that includes a PDF attachment with a copy of the signed consent form. The PDF will be emailed to Health Information Management from REDCap for incorporation into Epic.

To minimize the possibility of coercion or undue influence, potential participants will be given ample time to ask questions and review the consent form. In addition, it will be stressed that participation in this study does not alter the treatment course and that participation is completely voluntary. The potential participant will be provided with the name and contact information for the study coordinator and the PI and the Duke IRB in the event of questions or concerns after reviewing the consent.

8. Subject's Capacity to Give Legally Effective Consent:

Legally effective informed consent will be obtained for all subjects. “Legally effective” means that the subject 1) has sufficient information to make a decision, 2) understands the consequences of a decision, (3) is able to make a decision, and 4) is able to communicate a decision. If a potential subject is incapable of informed decision-making, consent from their legally authorized representative (LAR) will not be sought, as the cognitive-communication skills necessary for informed consent are also necessary for participation in the research. The study will include high functioning ALS patients who may not be able to physically sign the ICF due to disease related muscle weakness so we will include an LAR and witness signature line.

9. Study Interventions:

During the 12-week intervention period, participants will complete a home-based RMT program and participate in weekly web-based RMT therapy sessions (M8-M18). RMT will be divided into four 3-week cycles. Participants will begin RMT immediately after completing assessments during the pretest visit (M7; see **Figure 1**). During this visit, participants will demonstrate ability to complete RMT repetitions successfully, and will be provided with all the necessary training and equipment to complete home RMT for the next 12 weeks.

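### RMT trainers appear to stay with participants through the withdrawal phase with no check on their use, so an absence of decline in A2 cannot be told apart from continued training

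*Combined protocol and SAP*

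**What the plan says.** The study is a single-subject A1-B-A2 design with 12 participants. Section 4 (Design & Procedures) gives A2 its purpose: it "will determine detraining effects over 6 weeks of RMT withdrawal". Training fills the 12 weeks of B and ends at M19, week 18. MIP and MEP are then measured weekly by telehealth at M20-M24, with a last full assessment at M25, week 24.

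On equipment, section 4 states: "Following the fourth and final full assessment visit (M25), participants will return all equipment". No earlier return is described. For issue, section 4 says: "Prior to the pretest visit, participants who opt for remote visits will be mailed instructions for the home-based RMT regimen and the devices". Section 9 (Study Interventions) has participants equipped at M7, where they "will be provided with all the necessary training and equipment to complete home RMT for the next 12 weeks".

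On recording, section 9 says: "Participants will be asked to keep a paper log documenting the number of repetitions they complete each day". The log belongs to the home RMT programme. Section 13 places the weekly collection of safety information in the treatment phase. The A2 telehealth visits are described only as measuring MIP and MEP.

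Section 12 analyses MIP and MEP visually and with a single-subject d, once for baseline versus withdrawal and once for pretest versus posttest.

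**The concern.** The study has no concurrent control, so the comparison between phases carries the inference. A2 is informative about detraining only if training has stopped. As section 4 reads, each participant keeps an inspiratory and an expiratory trainer at home for the six weeks in which none is to be used. The document describes no question or log entry that would show whether one was used.

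The result at risk is a specific one. If pressures hold up in A2, the natural conclusion is that gains outlast training. Continued training would give the same picture. Section 4 says the results will be used to refine the regimen, choose outcomes and plan the analysis of a larger study, so an unfounded conclusion about retention would carry forward.

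The early mailing to remote participants raises a separate and smaller issue, for A1. They may hold trainers while the baseline is still being measured, whereas participants seen on site are equipped at M7.

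**Working it through.** **Reading the text.**
1. Training stops at M19 (week 18) and equipment is returned after M25 (week 24). The gap is 24 − 18 = 6 weeks, the whole of A2.
2. What A2 needs at home is the pressure meter, for the weekly MIP and MEP. Section 9 describes the training equipment as serving 12 weeks of home RMT, and those weeks are over.
3. That the trainers are among the items kept is an inference from the words on returning all equipment and from the absence of any earlier return. It is the plain reading, but it is not stated outright.
4. Sections 4, 9, 12 and 13 describe no check on RMT use in A2.

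**Which planned quantities are exposed.** Section 12 defines d = (mean of second assessment − mean of first) / SD of first.
- Baseline versus withdrawal: the second mean comes from A2, so continued training would raise d.
- Pretest versus posttest: no A2 data enter, so what happens in A2 cannot change it.
- Visual analysis: continued training would flatten a fall in A2. It could not produce one.

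**Size, as an illustration.** The document gives no figure to reproduce. Assume, in A1 SD units and with the A1 mean set to 0, a gain g at M19. Assume a share L of it would be lost linearly over weeks 19-24, and that unrecorded training prevents a share f of that loss. Then

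d = (1/6) Σ over w = 1 to 6 of [g − (1 − f)·L·g·w/6] = g − (21/36)(1 − f)·L·g,

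and the fall seen by week 24 is (1 − f)·L·g.

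| g | L | d at f = 0 | d at f = 0.5 | d at f = 1 |
|---|---|---|---|---|
| 1.0 | 0.25 | 0.85 | 0.93 | 1.00 |
| 1.0 | 0.5 | 0.71 | 0.85 | 1.00 |
| 1.0 | 1.0 | 0.42 | 0.71 | 1.00 |
| 2.0 | 0.25 | 1.71 | 1.85 | 2.00 |
| 2.0 | 0.5 | 1.42 | 1.71 | 2.00 |
| 2.0 | 1.0 | 0.83 | 1.42 | 2.00 |

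For g = 1 and L = 1, d = 1 − 0.583 = 0.42 at f = 0, 1 − 0.292 = 0.71 at f = 0.5, and 1.00 at f = 1. On section 12's scale these are negligible, modest and large. The fall seen by week 24 is 1.0, 0.5 and 0 SD. Over the grid, going from f = 0 to f = 1 raises d by (21/36)·L·g, from 0.15 (g = 1, L = 0.25) to 1.17 (g = 2, L = 1).

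Section 12 labels withdrawal M19-M24, while Figure 1 puts M19 at week 18 and M20-M25 at weeks 19-24. I used weeks 19-24. With weeks 18-23 the factor is 15/36, and the g = 1, L = 1 row becomes 0.58, 0.79 and 1.00, in the same three bands.

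**A1.** Training before M7 would raise the A1 mean and lower the numerator of d. A rising baseline would also tend to widen its SD. Both make the baseline-to-withdrawal d smaller.

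**The case against.** The strongest reply is that holding a trainer is not using it. A2 is defined as withdrawal, RMT is prescribed for 12 weeks only, and section 5 requires the ability to follow directions. This stands. A reader might infer that A2 fails, or that some participants will probably carry on. The document supports neither. It gives no information on continued use, and the offer of clinical RMT after M25 could equally make a six-week wait easier to accept.

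It is also fair to say that the bias in A2 runs one way. A decline in A2 is not created by keeping the trainers, although disease progression remains a separate explanation for it. The pretest-to-posttest d is untouched. This stands too, and it limits the point to the absence of a decline and to a high baseline-to-withdrawal d.

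On A1, a reader might infer that early mailing inflates the apparent benefit. The direction is the opposite. Moreover, the mailing date is not given and may already fall close to M7, a written log is sent with the devices, the training target is first set at M7, and the weekly A1 measurements might show a rise.

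A reader might also take the RMT row of Figure 1 to mean that training runs to week 24. In the text form of the figure the columns are shifted, and the prose is clear that RMT lasts 12 weeks, so the row is no evidence either way.

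Finally, detraining is not one of the two objectives in section 2. That lowers the weight of the point. It does not remove it, because section 4 assigns A2 this purpose and section 12 plans an effect size on it.

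**Conclusion.** The concern holds in a limited form. On the plain reading of section 4, the trainers stay with participants through A2 and their use goes unchecked. Stable MIP or MEP in A2, or a high baseline-to-withdrawal d, therefore cannot be separated from continued training. The text shows an unmonitored risk; it does not show that withdrawal was breached or that A2 is uninformative.

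The size cannot be derived from the document. Under the stated assumptions (linear loss, gain of 1 or 2 baseline SD), a participant whose continued training prevented all loss would show a d higher by 0.15 to 1.17. How many participants this would affect is unknown, and the plan collects nothing that would tell.

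The unstated mailing date for remote participants is a secondary weakness of A1. It creates a difference between remote and on-site participants and would, if anything, reduce the baseline-to-withdrawal d. The change is worth making because it is cheap and because unrecorded use cannot be reliably recovered afterwards.

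**What to change.** In section 4, replace the single return after M25 with two steps: both RMT trainers are handed in at M19, or mailed back that week if M19 is remote, and only the pressure meter is kept until M25.

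At each of M20-M25, ask and record whether any RMT was done since the last contact. Before M7, ask the same of anyone already holding a trainer. In section 12, state that the A2 comparison will be shown with and without participants who report use.

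If collection at M19 proves impractical, the question alone would make reported use visible, within the limits of self-report.

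The cost is one changed sentence in section 4, one added in section 12, a return mailer, one question, mostly at visits already scheduled, and a mail-back task for people with ALS or their caregivers. Anyone who starts clinical RMT after M25 would need a trainer issued again.
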